4.2 Exclusion Criteria

Study candidates who meet any of the following criteria within 28 days prior to entolimod administration will not be eligible for participation in this study:

1. Receipt of any other vaccines within the past 30 days prior to enrollment
2. Acute illness within the last 7 days without systemic signs and symptoms including fever > 99.5
3. History of hypersensitivity to the flu vaccine or its components (including gelatin, formaldehyde, octoxinol, thimerosal, and chicken protein).
4. History of Guillain Barré syndrome (GBS)
5. History of bleeding disorders
6. Medical contraindication to treatment with vaccine as indicated by a history of autoimmune disease, immune deficiency, or hypersensitivity to other vaccines.
7. Unstable major cardiovascular, renal, endocrine, immunological or hepatic disorder
8. Systolic blood pressure (SBP) < 110 mmHg or orthostatic hypotension [>20 mmHg fall in SBP or >10 mmHg fall in diastolic blood pressure (DBP) with standing] at the time of screening.
9. Evidence of an ongoing systemic bacterial, fungal, or viral infection (including upper respiratory tract infections) (within 14 days prior to entolimod administration). **Note:** *Subjects with localized fungal infections of skin or nails are eligible.*
10. Baseline vital signs with \geq Grade 2 abnormalities
11. Significant cardiovascular disease (e.g., myocardial infarction, arterial thromboembolism, cerebrovascular thromboembolism, venous thromboembolism) within 6 months prior to study drug administration; symptomatic dysrhythmias or unstable dysrhythmias requiring

medical therapy; angina requiring therapy; symptomatic peripheral vascular disease; New York Heart Association Class 3 or 4 congestive heart failure; or uncontrolled Grade ≥ 3 hypertension (diastolic blood pressure ≥ 100 mmHg or systolic blood pressure ≥ 160 mmHg) despite antihypertensive therapy.

- a. Significant screening ECG abnormalities, including unstable cardiac arrhythmia requiring medication, atrial fibrillation, 2nd-degree atrioventricular (AV) block type II, 3rd degree AV block, or Grade ≥ 2 bradycardia (within 14 days prior to entolimod administration).
- 12. Inadequate hepatic function (within 14 days prior to entolimod administration):
 - a. Serum alanine aminotransferase (ALT) $\geq 3 \times$ upper limit of normal (ULN) (Grade ≥ 1).
 - b. Serum aspartate aminotransferase (AST) $\geq 3 \times$ ULN (Grade ≥ 1)

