 - c. Serum alkaline phosphatase (ALP) $\geq 5 \times$ ULN (Grade ≥ 2)
- 13. Serum bilirubin $\geq 1.5 \times$ ULN (Grade ≥ 1)
- 14. Positive antiviral serology:
 - a. Positive hepatitis C virus (HCV) antibody or positive HCV ribonucleic acid (RNA) by quantitative PCR.
 - b. Positive hepatitis B surface antigen (HBsAg) and negative hepatitis B core (HBc) antibody or undetectable hepatitis B (HBV) deoxyribonucleic acid (DNA) by quantitative polymerase chain reaction (PCR) testing.
- 15. Positive human immunodeficiency virus (HIV) antibody.
- 16. Use of medication that might interact with the flu vaccine including (but not limited to) specifically: aminopyrine, phenytoin sodium, theophylline, and warfarin sodium.
- 17. Any ongoing treatment with immunosuppressive or immune-stimulant therapy
- 18. Ongoing use of systemic corticosteroids.
- 19. Blood or blood products given within the three months prior to vaccination and two months after vaccination
- 20. Current and/or expected receipt of chemotherapy, radiation therapy or any other cytotoxic or immunosuppressive therapy [i.e. more than 10 mg of prednisone given daily or on alternative days for 2 weeks or more in the past 3 months]
- 21. Receipt of another investigational pharmaceutical product within 60 days of treatment
- 22. Diagnosis of Parkinson's Disease, previous stroke, or significant cognitive impairment (defined as MMSE < 20)
- 23. Other concerns that in the opinion of the PI would preclude a subject from participating in study procedures or from completing the study.

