4.4 Early Withdrawal of Subjects

4.4.1 When and How to Withdraw Subjects

The following conditions describe the circumstances under which a subject may be withdrawn from the study prior to that subject completing all of the study related procedures:

- Any SAE that precludes further participation of the subject;
- With respect to subjects that have not received study drug, any SAE related to the study drug that in the opinion of the principle investigator or monitors as part of the Data and Safety Monitoring Plan (DSMP) which places subjects at high risk of experiencing the same SAE.
- If in the opinion of the principle investigator, there is doubt that a subject, for any reason, can continue to fully participate in the study; and
- Subject decision to withdraw from the study (withdrawal of consent).

See also Section 10.1, “Study Monitoring Plan”.

In the event of a subject withdrawal, the following will be performed:

- Review of data collected through the last in-person or remote visit for completeness;
- Replacement of study subject if the subject did not receive study drug (i.e., early withdrawal before study drug administration); and
- Follow-up for subjects withdrawn from study, if the treatment visit was completed. The exit visit will include those study assessments and procedures that would have been performed at the next scheduled visit.

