Recommendations with regard to specific types of concomitant therapies, supportive care, diet and other interventions are provided in the protocol. To minimize variations in supportive care, the recommended supportive care agents (e.g., loperamide, granisetron) should be used unless there is a medical rationale in a specific subject for use of an alternative product.

Anti-inflammatory or Antipyretic Drugs or Corticosteroids

Anti-inflammatory or antipyretic drugs may not be administered prophylactically. Thereafter, subjects may receive ibuprofen, 400 mg orally, as needed every 4 to 6 hours in response to constitutional symptoms, fever or malaise occurring following study drug administration. Other nonsteroidal anti-inflammatory drugs (NSAIDs) may be substituted as medically necessary. Post-entolimod use of acetaminophen, 650 mg orally as needed every 4 to 6 hours, may be used in response to constitutional or pyretic symptoms if medically necessary, but use of acetaminophen is not encouraged given its potential for adverse hepatic effects.

The use of systemic, topical, inhaled, or enteric corticosteroids during screening or on Day 1 should be avoided given that such drugs may confound interpretation of safety and pharmacodynamic responses in subjects on this study. However, such drugs are permitted after study drug administration if a subject develops an intercurrent condition that require corticosteroid therapy.

Support for Hypotension

In the event that a subject experiences hypotension (SBP <90 mm Hg or DBP <60 mm Hg; a > 20 mm Hg drop in SBP or > 10 mm Hg drop in SBP with symptoms at any time after administration of study drug or with orthostatics) it may be managed according to standards of

care until the SBP is ≥ 90 mmHg and the DBP is ≥ 60 mmHg on ≥ 2 determinations obtained ≥ 1 hour apart [or until BP approaches within 10% of baseline (pre-study drug values) with resolution of symptoms]. It should be emphasized that a subject's clinical condition, rather than blood pressure alone, should be the primary basis for any intervention or medical decision-making.

- As much as possible, subjects should be kept at rest following study drug administration.

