7.2 Statistical Methods

The full analysis dataset will be based on a modified intent-to-treat principle. Randomized subjects receiving blinded study drug will be included and analyzed based on their randomized assignment. Patients meeting exclusion criteria or withdrawing after initial screening and randomization are excluded from all analyses. Safety outcomes will analyze patients based on treatment received. Evaluable analysis sets will be defined and will include data from subjects who have the necessary baseline and on study measurements to provide interpretable results for specific parameters of interest.

Descriptive Statistics

Data will be described and summarized by study drug assignment (entolimod 1 μ g, 3 μ g, 10 μ g, or placebo) and time point. Descriptive summaries will include sample size, mean and standard deviation, median, 25th and 75th percentiles, minimum and maximum for continuous variables and percentage for categorical variables. Baseline/screening data will be summarized by randomized group using median (25th-75th) percentiles and percentage for continuous and categorical data, respectively. Study drug administration, concomitant medication use, supportive care use, AEs, laboratory abnormalities, vital signs/oxygen saturation, body weight, virology data, quality of life and frailty index status will be described and summarized.

Primary Hypothesis: We hypothesize that entolimod will cause an increase in influenza antibody titers at 4 weeks in comparison to placebo

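### Exclusion item 19 reaches two months past dosing, and Section 7.2, read literally, would then drop a treated subject from all analyses because of a post-randomization event

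*Combined protocol and SAP*

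**What the plan says.** Section 4.2 opens its list with a time frame and a target group: "Study candidates who meet any of the following criteria within 28 days prior to entolimod administration will not be eligible". Item 19 of the same list reads "Blood or blood products given within the three months prior to vaccination and two months after vaccination".

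Section 7.2 defines the analysis sets in three consecutive sentences:

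- Inclusion: "Randomized subjects receiving blinded study drug will be included and analyzed based on their randomized assignment".
- Exclusion: "Patients meeting exclusion criteria or withdrawing after initial screening and randomization are excluded from all analyses".
- Safety: "Safety outcomes will analyze patients based on treatment received".

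The primary contrast is the 4-week titer (Section 7.2), collected at the Month 1 visit, which has a window of one week either side (Table S-1). Safety is a primary objective and a primary endpoint alongside immunogenicity (Sections 2 and 3.4).

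Section 4.4.1 does not name blood products as a reason for withdrawal, but allows withdrawal where "there is doubt that a subject, for any reason, can continue to fully participate in the study". For treated subjects who are withdrawn it requires "Follow-up for subjects withdrawn from study, if the treatment visit was completed".

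**The concern.** A criterion that depends on what happens after dosing cannot decide who enters. Its only possible effect on a subject already treated is through the rule on analysis sets, and that rule refers to exclusion criteria without any limit to the pre-dose period. If it is applied as written, membership of the modified intent-to-treat and safety sets depends on an event after randomization. That weakens the protection randomization gives to the comparison with placebo. It could discard a primary titer that the blood product cannot have influenced. It could also take a subject out of the final safety summary when the reason for the blood product was itself an adverse event. Two analysts working in good faith could build different analysis sets from the same data.

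**Working it through.** The plan gives no figure on this point, so the main check is a comparison of the texts. Short arithmetic on size follows.

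1. **Timing of item 19.** Vaccine and study drug are given within one minute of each other (Section 5.2). The two months after vaccination are therefore two months after dosing, entirely outside the 28 pre-dose days of the lead-in.

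2. **Position of the primary titer.** The Month 1 draw falls about halfway through the two-month window. A blood product given after that draw and before two months cannot have affected the 4-week titer, yet it would still meet item 19.

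3. **The Section 7.2 sentences set against each other.** Take a subject who is randomized, dosed, has the Month 1 draw, receives a blood product at week 6 and stays in the study.
   - Under the inclusion sentence the subject is in, because study drug was received.
   - Under the exclusion sentence, read literally, the subject is out. Meeting an exclusion criterion and withdrawing are joined by *or*, so no withdrawal is needed, and the consequence covers all analyses.
   - Under the safety sentence the subject is analyzed by treatment received, unless already removed by the sentence before it.

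4. **Does the rest of the plan settle it?** Section 4.4.1 replaces only undosed subjects and follows treated ones. Section 7.2 handles missing primary data as missing at random, with imputation to the baseline value in a secondary approach. Both suggest that the exclusion sentence was meant for undosed subjects. However, the inclusion sentence already omits undosed subjects, so on that reading the exclusion sentence adds nothing. Section 4.4.1 also states a pre-dose limit explicitly where it means one, and the Section 7.2 sentence has none. The point is left open.

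5. **How many subjects.** The documents give no rate of blood-product use. For an assumed rate p, with subjects independent, the expected number is 100p and the chance of at least one is 1 − (1 − p)^100:

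| Assumed p | Expected of 100 | Chance of at least one |
|---|---|---|
| 0.5% | 0.5 | 39% |
| 1% | 1 | 63% |
| 2% | 2 | 87% |
| 5% | 5 | 99% |

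6. **What one removal does.**
   - Safety: if the removed subject had the only serious event in an arm of 25, the observed rate goes from 1/25 = 4% to 0/24 = 0%. This is a hypothetical case.
   - Power for A/H1N1, from the Section 7.1 inputs: log SD = √ln(1 + 2.0²) = 1.269, difference = ln 2 = 0.693, one-sided t-test at 0.15. With 25 against 25 this gives 81.2%; with 24 against 25 it gives 80.6%. Section 7.1 states 90% for the first case, which these inputs do not reproduce. That is a separate matter and does not affect this point.

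**The case against.** The strongest reply is that the exclusion sentence concerns subjects who were never dosed. It follows a sentence that includes all dosed, randomized subjects. Section 4.4.1 keeps treated subjects under follow-up, and the missing-data rules would have little purpose if dropouts were deleted. This reading is reasonable. For that reason, a reader who infers that the plan definitely removes such subjects goes further than the documents allow.

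Item 19 can also be read as an entry question about planned receipt. Item 20, just below it, speaks of current or expected receipt, and a subject at week 6 is no longer a candidate. That reading would remove the timing conflict, but item 19 itself refers to products given, not expected.

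Three further inferences are tempting and not supported:

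- **That such a subject cannot be withdrawn.** Blood products are not a listed reason, but discretionary withdrawal is open.
- **That serious events would escape safety oversight.** The DSMB receives all adverse event reports (Section 8.5.1) and reviews serious ones within 24 hours (Section 10.1), whatever the analysis set. At most the final analysis is affected. That a transfused subject has had a serious event is also an assumption.
- **That corticosteroid users are kept in the analyses by contrast.** The Supportive Care text says only that "such drugs are permitted after study drug administration if a subject develops an intercurrent condition that require corticosteroid therapy". It says nothing about any analysis set.

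The entry criteria (medically stable, no hospitalization in six months, no bleeding disorder, no warfarin) also make it likely that few subjects are affected.

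**Conclusion.** The point holds as an unresolved contradiction. Item 19 contains a post-dose condition that its own lead-in cannot accommodate, and Section 7.2 gives two instructions for a dosed subject who later meets it. Under the literal reading, a post-randomization event decides whether that subject counts for efficacy and safety.

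The size is small. The number affected rests wholly on an assumed rate, and losing one subject costs about half a percentage point of power (81.2% to 80.6%). The point is worth correcting because the analysis sets should be unambiguous before unblinding, because the subjects at risk of removal are selected by a post-dose event, and because the correction takes only a few sentences.

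**What to change.** Reconcile Section 4.2 (lead-in and item 19) with Section 7.2:

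1. Word item 19 so that it can be assessed at entry: prior receipt, and planned receipt if the sponsor intends that. An entry screen for planned blood products need not be lost.
2. Amend the Section 7.2 exclusion sentence so that it covers only subjects who did not receive study drug.
3. Add that events after dosing, including receipt of blood products, never remove a dosed subject from the modified intent-to-treat set or the safety set.
4. Record post-dose blood products, with dates, as concomitant therapy. Keep all titers drawn before them. Address titers drawn after them in a sensitivity analysis, for example by setting those values to missing in the mixed model, because donor antibody may be present.

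The cost is a few sentences of text and one extra sensitivity analysis. No new visits are needed, since concomitant therapy and adverse events are already reviewed at every site and remote visit (Sections 5.6 and 6.15).

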4.3 Subject Recruitment, Enrollment and Screening

Recruitment sources include: 1) Mayo Clinic Patients 2) Mayo – RST Classified Advertising 3) Flyers within the community, 4) Newspaper and Radio Advertising, 5) Existing lists/databases of individuals interested in being contacted about participation in research studies, and 6) Social Media including Facebook. Subject recruitment and advertisement will occur on Mayo campus and at various sites off campus (e.g., retirement centers). Permission will be obtained from each location before recruitment begins.

All patients who meet eligibility will be invited to participate in the study. Potential subjects will be approached by trained clinical coordinators who will assist in recruitment and carry-through of the protocol. Written and informed consent will be obtained by appointed, trained study personnel. Please see Inclusion and Exclusion criteria above. Documentation of recruitment and enrollment efforts will be maintained in a secure institutionally-supported database. Only those subjects who provide informed consent will be enrolled in the study; we anticipate enrolling 100 subjects.

4.4 Early Withdrawal of Subjects

4.4.1 When and How to Withdraw Subjects

The following conditions describe the circumstances under which a subject may be withdrawn from the study prior to that subject completing all of the study related procedures:

- Any SAE that precludes further participation of the subject;
- With respect to subjects that have not received study drug, any SAE related to the study drug that in the opinion of the principle investigator or monitors as part of the Data and Safety Monitoring Plan (DSMP) which places subjects at high risk of experiencing the same SAE.
- If in the opinion of the principle investigator, there is doubt that a subject, for any reason, can continue to fully participate in the study; and
- Subject decision to withdraw from the study (withdrawal of consent).

See also Section 10.1, “Study Monitoring Plan”.

In the event of a subject withdrawal, the following will be performed:

- Review of data collected through the last in-person or remote visit for completeness;
- Replacement of study subject if the subject did not receive study drug (i.e., early withdrawal before study drug administration); and
- Follow-up for subjects withdrawn from study, if the treatment visit was completed. The exit visit will include those study assessments and procedures that would have been performed at the next scheduled visit.

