6.4 Visit 4, Safety Follow-up –Day 7 (remote visit)

This visit will be recorded as “Day 7” and will be a remote visit where the following tests will be performed:

- Review of medications
- Review of adverse events
- Respiratory infection assessment
- Quality of Life (QoL) questionnaire

6.5 Visit 5, Follow-up - Month 1

This visit will be recorded as “Month 1” and will require a visit to the research center where the following tests will be performed:

- Vital signs (orthostatic blood pressure, oxygen saturation temperature, respiratory rate, weight, and heart rate)
- Review of medications
- Review of adverse events
- Respiratory infection assessment
- Quality of Life (QoL) questionnaire
- ECG
- Blood work – labs [serum chemistry, Hematology, coagulation, CMV, cytokines, vaccine related antibodies, LINE-1, peripheral blood mononuclear cells (PBMCs) and biomarkers of senescence]
- Urine collection for urinalysis

6.6 Visit 6, Follow-up – Month 2

This visit will be recorded as “Month 2” and will require a visit to the research center where the following tests will be performed:

- Vital signs (orthostatic blood pressure, oxygen saturation temperature, respiratory rate, weight, and heart rate)
- Review of medications
- Review of adverse events
- Respiratory infection assessment
- Quality of Life (QoL) questionnaire
- ECG
- Blood work – labs [serum chemistry, Hematology, coagulation, cytokines, vaccine related antibodies, LINE-1, and peripheral blood mononuclear cells (PBMCs)]
- Urine collection for urinalysis
- Frailty Assessments (includes questionnaires, physical function testing and body composition)

6.7 Visit 7, Follow-up – Month 6

This visit will be recorded as “Month 6” and will require a visit to the research center where the following tests will be performed:

- Vital signs (orthostatic blood pressure, oxygen saturation temperature, respiratory rate, weight, and heart rate)
- Review of medications
- Review of adverse events
- Respiratory infection assessment
- Quality of Life (QoL) questionnaire
- ECG
- Blood work – labs [serum chemistry, Hematology, coagulation, CMV, cytokines, LINE-1, and vaccine related antibodies]
- Urine collection for urinalysis
- Frailty Assessments (includes questionnaires, physical function testing and body composition)

6.8 Visit 8, Follow-up – Month 12

This visit will be recorded as “Month 12” and will require a visit to the research center where the following tests will be performed:

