10.1 Study Monitoring Plan

This study will utilize a Data and Safety Monitoring Board (DSMB) to provide a system for appropriate oversight and attention to the protection of human subjects and quality assurance. The DSMB will have the following monitoring activities: (1) Review of a pre-specified safety assessment after 6 subjects in each arm have completed safety follow-up period day 1; If the DSMB determines that it is safe to proceed the next dose will be administered and a safety assessment will be performed to determine if it is safe to continue to the highest dosing of 10ug; (2) prospective review of any issues related to the safety of subjects; and (3) regular review (i.e., twice yearly) of measures designed to protect the validity of the data and the integrity of the research study. With regard to monitoring activity (2), safety issues will include the timely review of all SAEs (within 24 hours) and the regular review (every 3 months) of all AEs. With regard to monitoring activity 3, the DSMB will review with the principle investigator and lead study coordinator the methods in which data is collected, stored, and protected, including review of randomly selected subject case report and other forms. The DSMB will also identify when to terminate a subject's participation by following prescribed individual stopping rules and when to terminate the study by following prescribed study stopping rules. Prescribed individual stopping rules will include the following: (1) Any SAE that precludes further participation of the subject; (2) With respect to subjects that have not received study drug, any SAE related to the study drug that in the opinion of the principle investigator or DSMB places subjects at high risk of

experiencing the same SAE; (3) if in the opinion of the principle investigator, there is doubt that a subject, for any reason, can continue to fully participate in the study. Prescribed study stopping rules will include the following: (1) dose-limiting toxicities as defined elsewhere in this document in ≥ 2 subjects for the lowest dose concentration of study drug. See also section 8.4, *Stopping Rules*. This will not preclude the analysis of pre-existing data.

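### A dosed subject withdrawn between Day 1 and Day 7 gets an exit visit copied from the remote Day 7 visit, with no vital signs, laboratory tests or ECG, and 7.2 as worded would drop such subjects from every analysis

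*Combined protocol and SAP*

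**What the plan says.** Section 10.1 has the DSMB end a subject's "participation by following prescribed individual stopping rules". There are three such rules. Rule (1) is an SAE that precludes participation. Rule (2) is limited by its opening words, "With respect to subjects that have not received study drug". Rule (3) applies where "there is doubt that a subject, for any reason, can continue to fully participate in the study". Rules (1) and (3) carry no such limit, so they reach dosed subjects. Section 4.4.1 lists the same grounds plus withdrawal of consent, in permissive terms, and points across: "See also Section 10.1".

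For a subject already dosed, 4.4.1 provides "Follow-up for subjects withdrawn from study, if the treatment visit was completed" and then defines the content: "The exit visit will include those study assessments and procedures that would have been performed at the next scheduled visit". Section 4.4.2 repeats this rule and adds no minimum set of tests. It does give a purpose: withdrawal may be drug-related, so later assessments can matter for both safety and outcomes.

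In the numbering of section 6 (dosing on Day 0), the visit after Day 1 is Visit 4 on Day 7, "and will be a remote visit where the following tests will be performed". The list there is medications, adverse events, respiratory infection and quality of life. In Table S-1 the Visit 4 column is blank for vital signs, ECG, all laboratory rows and vaccine antibodies, and the note to Figure 2 also makes Day 7 remote.

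Section 7.2 puts every randomized subject who received blinded drug into the full analysis set. Its next sentence removes from all analyses those who withdraw after screening and randomization.

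**The concern.** Safety at age 65 and over is a primary objective. Section 3.4 counts laboratory abnormalities, oxygen saturation, vital signs and ECG findings in the primary safety endpoint. Of the six potential risks named in 1.6, five are vital-sign or laboratory findings: lower blood pressure, faster heart rate, raised transaminases, hyperglycemia and hypophosphatemia. Section 1.4.2.1 describes the earlier hyperglycemia as asymptomatic and most blood pressure changes as unnoticed by subjects. A telephone interview would not find these.

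Rules (1) and (3) select subjects who have had an SAE or are becoming less able to take part, so missing measurements in them are unlikely to be random with respect to safety. The drug is given once, so withdrawal does not reduce exposure. What stops is study procedures and data. A subject withdrawn in the first week also has no Month 1 titer, which is the primary outcome.

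If 7.2 is then read literally, the same subject leaves the safety analysis altogether.

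**Working it through.** The plan states no figure on this point. The check applies the 4.4.1 rule to the visit lists in 6.2 to 6.9 and to Table S-1. After dosing, laboratory tests and ECG are scheduled at Day 1 and Months 1, 2, 6 and 12, which makes five sets.

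| Withdrawn | Next visit | Vital signs, laboratory tests and ECG at exit | Sets already held |
|---|---|---|---|
| After dosing, before the Day 1 visit | Visit 3, on site | Yes | 0 of 5 |
| Day 1 to Day 7 | Visit 4, remote | No | 1 of 5 |
| Day 7 to Month 1 | Visit 5, on site | Yes | 1 of 5 |
| Month 1 to Month 2 | Visit 6, on site | Yes | 2 of 5 |
| Month 2 to Month 6 | Visit 7, or a phone visit | Yes, or no if phone visits count | 3 of 5 |
| Month 6 to Month 12 | Visit 8, or a phone visit | Yes, or no if phone visits count | 4 of 5 |

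**Length of the gap.** Take a month as 365/12 = 30.42 days.

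- Numbered visits only: 7 − 1 = 6 days.
- Counting the monthly phone visits (Months 3–5 and 7–11): 6 + 3 × 30.42 + 5 × 30.42 = 6 + 91.3 + 152.1 = 249.3 days, and 249.3/365 = 68%. Of these, 243.3 days fall after Month 2.
- Counting the two-weekly calls in Table S-1 footnote p, so that the next contact is on site only in the last 14 days before Months 6 and 12: 6 + (4 × 30.42 − 14) + (6 × 30.42 − 14) = 6 + 107.7 + 168.5 = 282.2 days, and 282.2/365 = 77%.

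The text does not settle whether phone contacts count. Section 6.9 calls them visits, and 4.4.1 asks for "Review of data collected through the last in-person or remote visit for completeness". Table S-1 gives them no visit number, and section 3 calls them phone interviews.

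**Section 7.2.** Each subject is 1/25 = 4% of an arm. As an illustration, if one dosed subject in an arm is withdrawn for an SAE, the full analysis set gives 1 of 25. The exclusion sentence read literally gives 0 of 24. The missing-data part of 7.2 points the other way: it keeps dropouts in a mixed model under missing at random and, in a secondary approach, gives most of them their baseline titer. Those provisions would have little to act on if dosed withdrawals were already excluded.

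**The case against.** The strongest reply is that little is lost.

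- **Same schedule as completers.** No subject who stays in the trial has scheduled vital signs, laboratory tests or ECG between Day 1 and Month 1, so within that week the leaver provides what completers provide. This stands for the week itself. Completers do go on to Month 1, and the leaver does not.
- **Early effects.** Half-life is about 3 hours, cytokines return to pre-dose levels within 7 to 12 hours and neutrophils by 5 days (1.4.2.1). The Day 1 visit therefore catches much of what is expected. This stands, and it limits the size of the loss.
- **Event capture continues.** Sections 6.15 and 8.1 keep adverse event and SAE follow-up going and require related abnormal results to be recorded. A reader might infer that SAEs in withdrawn subjects go unrecorded; these sections do not support that. They prescribe no tests at exit, however, and a value that is never measured cannot be recorded.
- **A floor, not a ceiling.** The exit rule says what the visit includes and does not forbid more, and section 6 allows extra tests. That is correct, but section 6 also says such data need not be collected.
- **Titer.** A reader might infer that a titer at exit would rescue the primary outcome. A sample in the first week is not a 4-week titer, and the primary model already handles the gap under missing at random.
- **The withdrawal grounds.** A reader might also infer that rules (1) and (3) should apply only to undosed subjects. That would remove the written grounds for ending participation when an SAE makes blood draws or physical testing unsuitable. The grounds should stay.
- **Section 7.2.** The exclusion may be meant for withdrawal before dosing. That is the sensible reading, but the sentence does not say so.

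**Conclusion.** The point holds in a limited form. For a dosed subject withdrawn between Day 1 and Day 7, the written exit visit prescribes no vital signs, laboratory tests or ECG, which does not serve the purpose stated in 4.4.2. The undisputed window is 6 days. This rests on section 6.4, the Figure 2 note and Table S-1 taking precedence over the section 3 overview, which lists week 1 among the on-site evaluations.

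A reader might take the 68% or 77% figure to mean that most of follow-up is unprotected. The documents do not support that. Both figures require unnumbered phone contacts to count as scheduled visits, and all but 6 of those days fall after Month 2, when the Month 1 titer and at least three of the five laboratory/ECG sets have been collected.

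The documents do not say how many subjects will be withdrawn this way. It is probably few, though with 25 per arm each one is 4% of the arm.

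The 7.2 wording is a separate defect and needs no assumed rate. Taken literally, it contradicts the sentence before it and the missing-data section. Whether anyone would apply it to dosed subjects is not known.

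**What to change.** Keep the withdrawal grounds in 10.1 and 4.4.1 as they are, and make three changes.

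1. In 4.4.1, state that a dosed subject who has not withdrawn consent remains in follow-up for the Table S-1 safety assessments and the Month 1 titer as far as able, by phone or from the medical record where an on-site visit is not possible. This, rather than an exit sample, is what protects the 4-week outcome.
2. In 4.4.1 and 4.4.2, state that the exit visit of a dosed subject who does leave includes adverse event review, vital signs, laboratory tests and ECG where feasible, whichever visit is next. This also removes the question of whether phone contacts count.
3. In 7.2, limit the exclusion of withdrawals by adding *but before receiving study drug*.

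The cost is a few sentences in 4.4.1 and 4.4.2, five words in 7.2, and one on-site visit with tests for each dosed leaver. Current stipends for on-site follow-up visits are $75, or $100 at Month 12. Subjects who stay in follow-up need only assessments already planned.
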